and the University of Alabama at Birmingham (UAB) 1917 HIV Clinic. The study focused on re-engagement to care among PLWH who had previously linked to care but who were not currently engaged at the time of the study (N=170). The BA2C intervention was based on a CDC-recognized EBI, ARTAS, which was the first RCT shown to significantly increase linkage to and retention in care among recently diagnosed PLWH.^{17, 82, 83} The ARTAS intervention consists of a brief, strengths-based case management/MI approach aimed at facilitating a close, supportive relationship between the CHW and participant and consists of up to five visits. BA2C, which was tailored and adapted to PLWH who dropped out of care, expanded on ARTAS to provide additional support over a longer period. Participants enrolled in the intervention arm received an initial face-to-face meeting with an assigned CHW prior to attending their first return HIV primary care visit and attended at least ten and up to 12 visits over six months in which the CHW worked collaboratively with participants to resolve any barriers to care. Depending on participant needs, the CHW may attend medical appointments with the participant and/or provide transportation. Participants in the control arm received standard of care. Study findings from BA2C showed that participants in both study arms improved across multiple outcomes (linkage to care 30 days after baseline; retention in care, ART prescription, and viral suppression at 12 months after baseline), but there was no statistically significant difference between groups. The lack of statistical significance was likely due to a small sample size and a 70% retention rate due to challenges participants had in attending study appointments. CHAMPS will build on the evidence-based premise of BA2C and the enhanced relationship between CHW and participants while adding an mHealth component to facilitate study retention, described below.

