Inclusion criteria: 1) Able to speak, read, and write in English or Spanish (at the New York City site only); 2) Aged ≥18 years; 3) Willing to participate in any assigned arm of the intervention; 4) Having been diagnosed with HIV ≥6 months ago; 5) Have an HIV-1 RNA level >200 copies/mL, or at least one “no-show” visit in the past 12 months, or report either not virally suppressed in the past 12 months or virally unsuppressed in the past 12 months; 6) Own a smartphone; and 7) Ability and willingness to provide informed consent for study participation and consent for access to medical records. **Participants are not eligible if they meet any exclusion criteria:** 1) Reside in a nursing home, prison, and/or receiving in-patient psychiatric care at time of enrollment; 2) Terminal illness with life expectancy <6 months; and 3) Planning to move out of the area in the next 12 months.

Inclusion consideration: We carefully considered including newly diagnosed patients (diagnosed <6 months) and have chosen to not include this subset of PLWH because: 1) Our piloted interventions did not include newly-diagnosed persons; 2) Newly-diagnosed individuals are treatment naïve and their adherence behaviors are unknown and may change frequently as they begin their ART regimen; and 3) The advent of rapid-start ART for newly-diagnosed individuals is currently under trial in both locations, providing an ART-initiation intervention for these individuals that could compromise our study results.

Recruitment Plan

We will enroll a minimum of 50% women or transgender women combined across sites and stop enrollment of men at 150 to meet this goal. We will track the reasons and demographic characteristics of those refusing to participate and examine those data as part of our ongoing monitoring and implementation evaluation activities (see Human Subjects).

We will use the following strategies for recruiting PLWH for all aims of the study; these approaches have been successfully used by our team in past studies.⁹⁴⁻⁹⁸ Planned offline and online recruitment venues include the following:

- **Clinic and Community Outreach:** Clinic social workers and peer outreach staff will distribute information about the study using flyers and electronic advertisement boards in clinic waiting rooms.

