We have estimated the statistical power for the primary outcome of viral suppression (viral load ≤ 200). We will recruit and enroll 300 participants (n=150 in each site) and use a 1:1 random assignment to the intervention arm and the control arm (i.e., 75 in each arm per site). We estimate the statistical power to examine efficacy of the intervention at six months for the total subjects. All power estimations are based on $\alpha=0.05$ and 2-sided tests and following assumptions: (1) an 80% retention rate, at each follow-up assessment for each study arm (based on our 86.1% retention rate in New York City WiseApp trial); (2) a correlation of 0.6 of outcome measure for participants at different time points of assessment; (3) an intra-cluster correlation (ICC) of 0.2 of participants of same study sites; and (4) 75% baseline viral suppression rate (based on preliminary data of the BA2C study).

For the total sample (n=300), the proposed study will have at least 80% power to detect a difference of 12% or greater in viral suppression. The 12% difference in viral suppression is equivalent to a small effect size (Cohen's D of 0.31). Therefore, the proposed study will have sufficient power ($\geq 80\%$) to detect a small effect size or greater. Based on findings from our BA2C and WiseApp interventions, we expect a combined improvement of 12% on viral suppression as compared to the control arm.

We have also estimated the statistical power to assess sustainability of the intervention at 12 months. For this analysis, we will conduct a non-inferiority test of viral suppression at Month 12 as compared to Month 6. This study will have at least 80% power to conduct a non-inferiority test with a margin of 10%.

Sampling approach to successfully enroll PLWH who are not optimally engaged in HIV Care: Using active and passive recruitment methods, the project coordinator at each site will oversee and participate in recruitment efforts. The study staff hired through this project and the peer-to-peer networking efforts at each site will be used to recruit study participants. Our study team at both sites has extensive experience in recruitment efforts for projects similar to the one proposed here and will be able to successfully recruit the study sample.

Eligibility Screening

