The distribution of all variables will be assessed, as will the correlations between all variables and the primary/secondary outcomes. We will assess for patterns of missing data, which are expected to be low as the study utilizes computer-assisted self-interview (CASI) for sensitive data, which reduces participant nonresponse. The primary anticipated reason for missing data is attrition due to loss to follow-up. Based on our preliminary studies, we are accounting for 20% attrition from randomization to the 12-month assessment.

All multivariate analyses will be preceded by standard descriptive bivariate analyses to describe key variables and relationships among them. These analyses will include means, frequency tables, histograms, and examination of distributions. All statistical tests will be two-sided tests with the level of significance at 0.05. The primary hypothesis 1 will be a comparison of viral suppression (primary outcome) between CHAMPS and standard of care. We will also compare the drop in viral load (measured in logarithmic scale with base 10) between the two groups. Our secondary and related outcome is ART adherence measured in two ways: 1) a single-item self-report measure, an empirically validated instrument (SRSI)¹⁰¹ and 2) electronic pill bottle data which we will be collecting in the intervention group since all participants will receive a CleverCap bottle for their medications. All the analyses will be based on initial assignment to groups, using the intention-to-treat principle.^{131, 132}

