The primary hypothesis 1 (H_1) will be tested using a generalized linear mixed model (GLMM) with logit-link function for binary outcomes (i.e., viral suppression) or a linear mixed model (LMM) for continuous outcomes (i.e., viral load measured in logarithmic scale) to account for the non-independence of repeated measurements within individuals.¹³³ The models will include a random intercept and fixed effects for intervention group, time, and interaction term of group and time which is for testing efficacy of the intervention. The model may include stratification variables, such as study site, age, and sex as covariates. A site by group interaction will be also examined and included in each model (above) if significant at the .05 level. All analyses will be tested for goodness-of-fit using the Wald-type test, which shows satisfactory performance for models with fewer (<5) covariates.¹³⁴ A similar GLMM will be used to test sustainability of the intervention at month 12. For this analysis, we will conduct a non-inferiority test¹³⁵ to compare viral suppression rate between month 12 and month 6. For primary hypothesis 2 (H_2), testing for intervention effect on ART adherence measured by SRSI (secondary outcome), we will use a similar LMM as mentioned above. For electronic pill bottle data in the intervention group, we will also examine the trend of electronic pill bottom data over time with a GLMM which will include a first-order autoregressive (AR1) covariance structure, as described by Hedeker and Gibbons.¹³³ We will also aggregate the electronic pill bottle data at different time points (0, 6, and 12 months) and examine the association between the electronic pill bottle data and ART adherence data measured by SRSI using Spearman nonparametric correlation.¹⁰¹ Similar GLMMs or LMMs will be used for secondary outcomes, with GLMMs for binary outcomes and LMMs for continuous outcomes.

Aim 2: Identify mediators and moderators of CHAMPS on study outcomes.

Data Analysis

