Missing data. Missing data may occur in the proposed study in several ways. First, it may occur due to item non-response. When missing data is limited to only a few items on a measure, we will prorate total scores for a measure by taking an average score on the measure and multiplying it by the total number of items in the scale. Missing data can also occur from attrition due to missed assessments or dropout from the study. Prior to performing any outcome analyses, we will evaluate the amount, reasons, and patterns of missing data. If the reason for missing data is not related to the outcome of interest, then they are considered to be missing completely at random, and complete case analysis will still generate unbiased estimates.¹³⁸ We will conduct sensitivity analyses to compare estimates of treatment effects with and without multiple imputation to assess the effect of missing data on statistical inference.

Aim 3: Guided by the Reach Effectiveness Adoption Implementation Maintenance (RE-AIM) framework, identify multi-level factors associated with successful implementation of CHAMPS to inform future implementation and scale-up.

Overview

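### The one planned missing-data sensitivity analysis, with versus without multiple imputation, cannot show whether the month-6 result withstands dropout that depends on the unobserved viral load

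*Combined protocol and SAP*

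**What the plan says.** All references are to the combined protocol and SAP.

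- **Missing data** (under Aim 2, Data Analysis). Scale scores are prorated for item non-response. The team will look at the extent, causes and pattern of missingness before any outcome analysis. A conditional remark follows: "If the reason for missing data is not related to the outcome of interest, then they are considered to be missing completely at random", in which case complete cases are said to be unbiased. The one sensitivity analysis is to "compare estimates of treatment effects with and without multiple imputation to assess the effect of missing data on statistical inference". No imputation model is given.
- **Data Analysis, Aim 1.** The primary outcome, viral load of 200 or below at month 6, is tested with a random-intercept logistic mixed model "to account for the non-independence of repeated measurements within individuals". No estimation method is named. Analysis is by intention to treat, with no rule for a missing month-6 viral load. On the cause of missingness: "The primary anticipated reason for missing data is attrition due to loss to follow-up". On its extent: "we are accounting for 20% attrition from randomization to the 12-month assessment".
- **Sample Size and Power Calculation.** Assumes "an 80% retention rate, at each follow-up assessment for each study arm", set below the 86.1% retention seen in the earlier WiseApp trial.
- **Eligibility Criteria.** One entry route is "at least one “no-show” visit in the past 12 months".
- **Preliminary Data, BA2C.** The earlier trial kept 70% of participants, and CHAMPS builds on it "while adding an mHealth component to facilitate study retention".

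No section specifies a delta-adjusted, tipping-point or pattern-mixture analysis, or a scenario that counts missing as not suppressed.

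**The concern.** The comparison is meant to show how missing data affect inference. A likelihood-fitted mixed model and standard multiple imputation are both valid when dropout depends only on observed data (missing at random). Complete-case analysis generally needs a stricter condition. None of the three allows for dropout that depends on the unseen month-6 viral load.

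Such dropout is plausible here. Loss to follow-up is the main expected cause of missing data, people can enter because they missed visits, and those who stop attending may also be those who stop taking treatment. Only one arm receives the mHealth component, which is expected to help retention, so the link between dropout and outcome may differ by arm. If it does, both sides of the planned comparison can be wrong in the same direction and still look alike. A reader would then take as reassurance something the analysis could not have contradicted.

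**Working it through.** **1. Inputs.** From Sample Size and Power Calculation: 150 per arm; 80% retention, so 120 observed and 30 missing per arm; 75% suppressed, plus 12 points. The plan calls the 75% a baseline rate; using it as the control rate at month 6 is my assumption. The plan's effect size reproduces: 2·asin(√0.87) − 2·asin(√0.75) = 0.309, against the stated 0.31. Rounded counts are 104/120 (86.7%) v 90/120 (75.0%).

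The 20% in Data Analysis is loss by month 12, so month-6 loss may be smaller. I therefore add about 14% missing (from the 86.1%: 129 observed, 112 v 97 suppressed) and an assumed 10% (135 observed, 117 v 101).

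**2. Method.** Unadjusted difference in proportions, not the mixed model. Without imputation, SE = √[p₁(1−p₁)/n + p₂(1−p₂)/n]. With imputation, each arm's rate is drawn from Beta(suppressed + 0.5, unsuppressed + 0.5), lowered by delta where stated, and missing outcomes are drawn binomially. Results are combined by Rubin's rules, T = W + (1 + 1/m)B.

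The effect of delta on the point estimate can be checked by hand. Lowering 30 missing participants by 10 points removes 0.10 × 30/150 = 2.0 points from that arm. The shift is 0.10 × 21/150 = 1.4 points at 14% missing and 0.10 × 15/150 = 1.0 point at 10%.

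| Missing per arm | Scenario | Difference (points) | SE | p |
|---|---|---|---|---|
| 20% | no imputation | 11.7 | 5.03 | 0.020 |
| 20% | standard imputation | 11.6 | 5.03 | 0.020 |
| 20% | CHAMPS lowered 10 | 9.6 | 5.20 | 0.064 |
| 20% | both lowered 10 | 11.6 | 5.31 | 0.028 |
| 20% | control lowered 10 | 13.6 | 5.14 | 0.008 |
| about 14% | no / standard imputation | 11.6 | 4.83 | 0.016 |
| about 14% | CHAMPS lowered 10 | 10.2 | 4.96 | 0.039 |
| 10% | no / standard imputation | 11.9 / 11.8 | 4.75 | 0.013 |
| 10% | CHAMPS lowered 10 | 10.8 | 4.84 | 0.025 |

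The planned comparison corresponds to the first two rows at each level of loss. It returns the same p-value whichever of the other rows is true.

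**3. Can the two sides share a bias?** A large-sample simulation used 20% missing per arm and an assumed correlation between baseline and month 6 of about 0.57. Control dropout was unrelated to outcome. Unsuppressed CHAMPS participants dropped out 2, 3 or 4 times as often as suppressed ones (an assumed range).

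- No true effect: complete cases gave +3.8, +6.4 and +8.1 points; missing-at-random imputation gave +2.6, +4.6 and +5.9.
- True effect of +12: about +14.5, +16.3 and +18.0, against +14.0, +15.5 and +17.0.
- Same 3:1 ratio in both arms: about zero bias with no effect; with a true +12, +10.3 (complete cases) and +11.3 (imputation), an attenuation.

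In the arm-differential cases both methods err in the same direction and lie about 0.5 to 2.2 points apart. That gap is small beside the standard errors of about 5 points in the table.

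**4. Missing counted as not suppressed (pooled z-test).** At 20% missing, 104/120 v 90/120 (z=2.30, p=0.022) becomes 104/150 v 90/150 (z=1.69, p=0.091). At 10%, 117/135 v 101/135 (p=0.014) becomes 117/150 v 101/150 (z=2.07, p=0.038).

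This rule also responds to retention alone. Take 60 missing in total and similar observed rates. With 24 CHAMPS and 36 control missing, 109/150 v 86/150 gives p=0.005. With the split reversed, 99/150 v 95/150 gives p=0.63.

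**The case against.** **The assumption is inferred.** A reader might say that the primary model and the sensitivity analysis rest on the same missing-at-random assumption. The documents do not support that. They never use the term, name no estimation method for the mixed model, and mention complete cases just before the with-and-without comparison. On the complete-case reading the two sides rest on different assumptions. This stands, and the claim here is only that neither side covers dropout that depends on the unseen value.

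**The plan does look at missingness.** It reviews the reasons and patterns before outcome analysis, and the RE-AIM table adds a review of withdrawal notes. These steps can reveal differential loss. They cannot test whether dropout depends on a value nobody observed. A richer imputation model, using adherence or month-12 viral load for example, could reduce the problem but could not rule it out.

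**The harm needs arm-differential dropout.** This largely stands. Lowering both arms by 10 points leaves p=0.028. The plan assumes equal retention and pays both arms equally, so a difference between arms is a risk rather than something the plan expects.

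**The direction is open.** This also stands. If the mHealth component keeps unsuppressed CHAMPS participants in follow-up while control loses them, the observed control rate is too high and the bias runs against CHAMPS. The control-lowered row (p=0.008) is that case.

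**The loss of significance depends on the amount missing.** This stands for the delta example: at about 14% or 10% missing, lowering CHAMPS by 10 points does not change the conclusion. Counting missing as failure dilutes any difference mechanically, so p=0.091 is not itself evidence of bias.

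**Conclusion.** The point holds in limited form. Followed exactly, the planned comparison cannot show whether the primary result is robust to dropout that depends on the unobserved month-6 viral load, and nothing else in the plan examines that. The mixed model remains a reasonable primary analysis.

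At the plan's 20% loss, a 10-point departure confined to CHAMPS moves p from 0.020 to 0.064, and the planned comparison would not register it. The same departure in both arms, in control only, or in CHAMPS with 14% or less missing leaves the result significant. These figures are unadjusted illustrations. They assume month-6 rates near 87% and 75%, equal loss by arm, imputation from arm alone and an arbitrary delta. They set no tipping threshold.

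Two further inferences are not supported. One is that the trial's result will be biased, or biased in favour of CHAMPS: the documents fix neither the size nor the direction. The other is that the plan assumes missing completely at random for its primary test: that sentence is conditional and does not govern the mixed model.

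The change should be made because it is cheap and lets the plan answer the question it sets itself.

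**What to change.** Keep the mixed model as primary. Add to the Missing data paragraph a prespecified delta-adjusted multiple-imputation analysis of month-6 suppression, with these elements:

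- the imputation model stated;
- delta varied in CHAMPS alone, in control alone and in both arms together, over a range justified before outcome data are analysed;
- results combined by Rubin's rules and shown as a tipping-point display;
- missing counted as not suppressed as one supporting scenario, reported with the number missing by arm and never alone, because it mixes retention with suppression.

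State also what the side without imputation is: the mixed model on all available data, or complete cases.

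The cost is modest extra analysis, with no new visits or blood draws. The delta range needs clinical justification in advance, and the result may look less robust than the current plan would make it appear.

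Two changes are optional and not part of the defect. The wording on missing completely at random could be tightened, since that condition also requires independence from observed data. Viral loads already collected from medical records could support a supplementary analysis, provided both arms use the same prespecified window.

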use, and safety in the field. The CHW will also be trained on use of the WiseApp and CleverCap assuring all study participants and CHW are able to successfully use the mHealth technology. Training for the CHW will also be provided on: human subjects research protection, financial conflict of interest, HIPAA, and data privacy and security. The CHW will engage in supportive strengths-based case management and MI with the study participant. Intervention visits (~ten over a six-month period) will help participants access primary medical care by acknowledging and addressing barriers to care.

Participants will have the option to participate in most CHW sessions in-person or via the App. This will help participants overcome many of the challenges to participating in-person, which was a frequent barrier in Birmingham and a current barrier due to COVID-19 in NYC.

The WiseApp offers the following functionality listed in Table 2, and the CleverCap is linked to the WiseApp. The CleverCap fits on standard pill bottles, dispenses only the prescribed amount of medication, keeps track of medications dispensed, and communicates wirelessly with mobile devices. Participants are then able to self-monitor their medications, and the CHW will also be able to track study participants' adherence to their ART medication in real time. Participants receive reminders through the WiseApp when they have not taken their medication on time and receive encouraging messages (e.g., Great job! You've met your goal for not forgetting your meds) when they have taken their medication. Communication, whether in-person or via the App, will enhance the relationship between the CHW and the study participant.

The sessions and sample content are illustrated in Table 3. CHAMPS is a manualized intervention and study visits focus on topic areas such as linkage to care, medication adherence, health literacy, access to support services, and HIV disclosure. Ideally session #1 will be in person and #6 needs to be in-person during the care visit.

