Efficacy: The impact of an intervention on outcomes including potential negative effects, quality of life.	
Did the intervention achieve primary and secondary outcomes?	Between-group comparisons on primary and secondary outcomes (Aim 1)
Did it produce unintended adverse consequences?	Review notes from participant study withdrawal, Notifications to the IRB about participant complaints
What effect did the mediators and moderators have on the primary and secondary outcomes?	Data analyzed in Aim 2
Adoption: The absolute number, proportion, and acceptability of CHAMPS; proportion of eligible patients that enroll.	
Did the intervention help the organization address its mission, values, and priorities?	Key informant interviews with clinic staff, research staff, CHW, and administration - descriptive, interpretative analysis for key themes
Implementation: At the setting level, includes consistency of delivery and predisposing, enabling, and reinforcing factors. At the individual level, implementation refers to individual's use of strategies. ¹⁵²	
Were intervention components delivered as intended?	Paradata Analysis –App use by component
What barriers to implementation were identified and how were they addressed?	Key informant interviews with study staff; In-depth interviews with study participants. - descriptive, interpretative analysis for key themes
What enabling (facilitating) factors were required to support the intervention?	Project meeting minutes Interviews with stakeholders
Maintenance: Individual – Understanding Use of the App over time.	
Did the intervention produce lasting effects at individual level?	Long-term efficacy of CHAMPS intervention over 12 months
Is there the potential for sustaining CHAMPS over time?	Key informant interviews with clinic staff, research staff, CHW and clinicians, CBO staff and study participants.
How did the intervention evolve?	Project meeting minutes; Paradata

implementation evaluation for this proposal; [name] will provide oversight, along with MPIs [name] and [name], for all implementation activities.

Process Evaluation Outcomes

The RE-AIM evaluation dimensions and associated measures in our study are summarized in Table 5. In addition to testing the **Efficacy** of CHAMPS, we will concurrently measure the four remaining RE-AIM dimensions¹⁵¹ as follows:

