A detailed monitoring plan will be included as part of the study protocol, submitted to the IRB, and reviewed and approved by the funding Institute and Center before the study begins. Prior to initiation of the study, agreement about the data safety monitoring plan will be confirmed to ensure the safety of subjects and the validity and integrity of the data. The research coordinator at each site will report serious adverse events (SAEs) that are unexpected and study-related immediately to a study physician who will convey this information to the study team, IRB, and NIH. All AEs and SAEs will be captured, reports will be completed, and information will be entered into the study database. A safety report will detail all serious and unexpected AEs or other unanticipated problems that involve risk to study participants or others and whether these appeared to be related to the study-based interventions or research assessment protocols. If the study team, CUIMC or UAB IRB, or NIH has concerns regarding SAEs, the Western IRB will be notified and a copy of the safety summary will be filed with both IRBs. Actions taken by the Western, CUIMC, or UAB IRB offices in response to AE concerns will be reported to the NIH. All AEs will be reviewed every six months, or sooner, with the designated safety officer.

Vulnerable Subjects:

Economically and/or educationally disadvantaged persons will be enrolled. While this group is considered a vulnerable population, the study team has considerable experience enrolling these participants. As these groups carry the burden of the majority of HIV incidence in both study sites and demonstrate considerable challenges with achieving optimal HIV health outcomes, it is important that they are not excluded from participation in this study. Additionally, our study will analyze the potential impact of the intervention(s) on racial and ethnic groups, perhaps providing new information on the disproportionate impact of HIV felt by these populations.

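### The Table 5 row on unintended adverse consequences relies on withdrawal notes and complaints alone, and nothing links it to the adverse event records or summarises those by arm

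*Combined protocol and SAP*

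**What the plan says.** Table 5 (Aim 3, RE-AIM dimensions and measures) puts harm inside the Efficacy dimension, which it defines as "Efficacy: The impact of an intervention on outcomes including potential negative effects, quality of life". One row under that dimension asks "Did it produce unintended adverse consequences" and lists two sources: "Review notes from participant study withdrawal, Notifications to the IRB about participant complaints". The row just above it, on the primary and secondary outcomes, is answered by comparing the groups. The harm row specifies no comparison.

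The section Unexpected and Serious Adverse Event Reporting describes a broader collection: "All AEs and SAEs will be captured, reports will be completed, and information will be entered into the study database". It adds that "A safety report will detail all serious and unexpected AEs or other unanticipated problems that involve risk to study participants or others", and that the report will state "whether these appeared to be related to the study-based interventions or research assessment protocols". All adverse events are reviewed with a safety officer at least every six months. A Data and Safety Monitoring Plan is said to be attached separately and is not part of these documents.

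Two other statements bear on the point. The Study Design section describes the CHAMPS contacts: "Intervention visits (~ten over a six-month period) will help participants access primary medical care". The sample size section assumes "an 80% retention rate, at each follow-up assessment for each study arm".

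**The concern.** Whether an intervention produced harm is a causal question, and a randomised trial can answer it from data by arm. The row does not do so. A person enters its answer by leaving the study or through a complaint that reaches the IRB. A participant whose HIV status is disclosed by accident, or who has trouble with the pill bottle or the app, but who stays and makes no complaint, contributes nothing.

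Such harms are foreseeable on the protocol's own account. Its risk section names breaches of confidentiality and discomfort with questions, and CHAMPS adds an app, a connected pill bottle, reminders and chat with the CHW.

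At stake is the trial's statement about adverse consequences. It would rest on a selected subset, while fuller records sit unused for this purpose in the study database.

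**Working it through.** The documents give no harm rate and no planned precision for harm, so there is no figure to reproduce. The check compares sections, followed by simple arithmetic for scale.

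**Step 1. Is the gap closed elsewhere?**

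- Table 5, harm row: two sources, with no mention of adverse event records.
- Adverse event reporting section: all events are captured, and the safety report addresses relatedness for serious and unexpected events and unanticipated problems. It gives no summary by randomised arm and does not refer to the Table 5 question.
- Data Analysis under Aims 1 and 2, including the missing data paragraph: no adverse event analysis.
- Data Analysis under Aim 3 (RE-AIM, paradata, interviews): no adverse event analysis.
- Table 4: no adverse event row.
- Table 6, the sample interview guide: no direct question on harm. The nearest prompts concern comfort with the app in social settings, stopping the app, and what to change. About 60 participants are to be interviewed.

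The records exist, but no section connects them to the question.

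**Step 2. How many participants can leave a withdrawal note?**

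Inputs: 300 participants randomised 1:1, so 150 per arm; 80% retention (sample size section).

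- Retained: 300 × 0.80 = 240 overall, 150 × 0.80 = 120 per arm.
- Not retained: 300 − 240 = 60 overall, 150 − 120 = 30 per arm.

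So about 240 of 300 would leave no note and can enter this row only through a complaint. The 60 is an upper bound on notes: the Data Analysis section expects missing data mainly from loss to follow-up, and people who are lost may leave no note.

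**Step 3. Illustration, with assumed harm rates.**

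Suppose harm occurs at rate p in the CHAMPS arm, is unrelated to leaving, and every leaver leaves a note. The chance of at least one case among n people is 1 − (1 − p)^n.

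| Assumed p | 30 leavers | All 150 in the arm |
|---|---|---|
| 1% | 1 − 0.99^30 = 26.0% | 1 − 0.99^150 = 77.9% |
| 2% | 1 − 0.98^30 = 45.5% | 1 − 0.98^150 = 95.2% |
| 5% | 1 − 0.95^30 = 78.5% | above 99% |
| 10% | 1 − 0.90^30 = 95.8% | above 99% |

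The middle column covers withdrawal notes alone; complaints would add cases. If harmed participants leave more often, the notes catch more. If leavers are simply lost, they catch fewer. The table shows direction and is not an estimate of the under-count.

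**Step 4. Would a raw comparison of recorded events by arm be fair?**

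CHAMPS participants have about ten CHW contacts in six months, and notes of those encounters are among the listed study data. Study visits for both arms are at screening, baseline, 6 and 12 months. If events are recorded as they come up, the CHAMPS arm has more occasions for one to surface. Linking the database to the row therefore needs a safeguard on how events came to light.

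**The case against.** The strongest reply is that the plan as a whole does count harm in people who stay and do not complain. The adverse event section captures every event with no condition on withdrawal or complaint, addresses relatedness for the serious and unexpected ones, and has all of them reviewed regularly. This stands. A reader might infer from Table 5 that the trial ignores such harms or makes no use of its adverse event data, and the documents do not support that inference. Table 5 is also a summary, and nothing says that its cells are exhaustive.

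A reader might also infer that adverse event capture is passive because Table 4 has no row for it. That is not shown. Elicitation may be set out in the separate monitoring plan, so the imbalance in Step 4 is conditional.

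Other sources could show some harms in both arms: the quality of life, symptom, stigma, depression and anxiety measures, and the medical records. The open prompts in Table 6 could do so in a sample of participants. The row cites none of these. Nor does it require a participant to write to the IRB; a complaint made to staff and then notified would fit.

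Finally, the trial is described as minimal risk, and no hypothesis, test or sample size depends on this row. That limits the weight of the point. It does not supply the missing link or a summary by arm.

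**Conclusion.** The point holds for the Table 5 row. As written, the row relies on two sources that select on leaving or complaining, and no section of these documents uses the adverse event records for the question or tabulates them by randomised arm. With about 240 of 300 participants expected to leave no withdrawal note, the row under-counts harm. That number rests on the planned 80% retention. How much harm would be missed cannot be derived, since it depends on harm, complaint and note-leaving rates that the documents do not give. Any stated fraction would rest on assumed rates and would credit the adverse event database with nothing.

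This is a minor to moderate point about how harm is reported. The primary analysis is unaffected.

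**What to change.** In the Table 5 row, add the study's adverse event database as a source, tabulated by randomised arm and by relatedness. Keep withdrawal notes and complaint notifications as supplements.

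Then deal with unequal contact in one of two ways:

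- Flag events that surfaced only through CHW contacts and report them separately from the rest.
- Unless the Data and Safety Monitoring Plan already provides for equal elicitation, ask one identical adverse event and social harm item, including unintended disclosure of HIV status, in both arms at 6 and 12 months. Add it as a row in Table 4 and base the between-arm comparison on it. The database table then stays descriptive.

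If the monitoring plan already sets out equal elicitation, a cross-reference to it plus the table by arm is enough.

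The cost is low. The table uses data already to be collected, and the optional item would be asked at visits that already take place. The downside is about a minute per visit and more minor events to log.
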